Appendix 8. Guidelines For Safety Monitoring And Discontinuations

For the purpose of safety monitoring for serum creatinine, creatinine clearance (CrCl) and hemoglobin levels in Study A3921145, baseline values are defined as:

- For subjects who enroll in study A3921145 on the same day and within 14 days following previous participation in there tofacitinib qualifying/index study.
 - For serum creatinine, the average of qualifying/index study screening and baseline visit values will be used.
 - For creatinine clearance, the average of qualifying/index study screening and baseline visit values will be used.
 - For hemoglobin, the qualifying/index study baseline visit value will be used.
- For subjects who enroll in study A3921145 greater than 14 days after participating in the tofacitinib qualifying/index study.
 - For serum creatinine, the average of A3921145 screening and baseline visit values will be used.
 - For creatinine clearance, the average of A3921145 screening and baseline visit values will be used.
 - For hemoglobin, the A3921145 baseline visit values will be used.

The following laboratory abnormality requires monitoring:

- Increased lipid parameters (total cholesterol, LDL cholesterol, HDL cholesterol, triglycerides) should be monitored and treated according to local guidance (eg, diet and behavior modification, statin therapy).

The following laboratory abnormalities require prompt retesting, ideally within 3-5 days:

- Lymphocyte counts <500 lymphocytes/mm³.
- Neutrophil counts <1000 neutrophils/mm³.
- **Applicable to Investigative Sites in the UK and Belgium:** Study drug will be discontinued temporarily for confirmed absolute neutrophil counts (ANC) levels of 500 – 1000 neutrophils/mm³. The subject will be monitored closely through unscheduled visits and laboratory retesting until ANC is >1000 neutrophils/mm³. Dosing may be resumed when ANC returns to >1000 neutrophils/mm³.

- Platelet counts $<100,000$ platelets/ mm^3 .
- Any single AST and/or ALT elevation >3 times the upper limit of normal (repeat laboratory testing must include CK, Total Bilirubin, Direct and Indirect Bilirubin, GGT, INR and alkaline phosphatase), regardless of the total Bilirubin.
- Any single hemoglobin value <8.0 g/dL.
- Any single hemoglobin value that is ≥ 2 gm/dL below the baseline (defined above) within the first 12 months of participation in A3921145. For the decreased hemoglobin (≥ 2 gm/dL below baseline) still within the reference range, retesting hemoglobin can be performed once prior to the next scheduled study visit.
- After the first 12 months of participation in A3921145, any hemoglobin value that is ≥ 2 gm/dL below the highest hemoglobin level reported within the previous 12 month period.
- Any single increase in serum creatinine $>50\%$ over the average of screening and baseline values (as defined above) OR an absolute increase in serum creatinine $\geq 0.5\text{mg/dL}$ ($\geq 44.2 \mu\text{mol/L}$) over the average of screening and baseline values (as defined above)

AND

Any single CrCl decrease of $>30\%$ over the average of screening and baseline values (as defined above)

(N.B. Screening and baseline values to be used for this monitoring criteria are defined at the beginning of [Appendix 8](#))

Tofacitinib Temporary Withholding or Discontinuation for Venous Thromboembolism:

- Per Amendment 10, for subjects with suspected venous thromboembolism, treatment with tofacitinib should be temporarily withheld while the subject is evaluated. If venous thromboembolism is confirmed, discontinue treatment with tofacitinib and withdraw the subject from the study.

Treatment with tofacitinib will be discontinued and the subject withdrawn from this study for:

- Serious infections (those requiring parenteral antimicrobial therapy or hospitalization).
- Two sequential lymphocyte counts <500 lymphocytes/ mm^3 ;
- Two sequential neutrophil counts <500 neutrophils/ mm^3 .
- Two sequential platelet counts $<75,000$ platelets/ mm^3 .

- Two sequential AST or ALT elevations >3 times the upper limit of normal with at least one Total Bilirubin value >2 times the upper limit of normal.¹
- Two sequential AST or ALT elevations >3 times the upper limit of normal with an abnormal INR.¹
- Two sequential AST or ALT elevations >3 times the upper limit of normal accompanied by symptoms consistent with hepatic injury.¹
- Two sequential AST or ALT elevations >5 times the upper limit of normal, regardless of Total Bilirubin or accompanying symptoms.¹
- Single positive HBc Ab and a negative HBs Ab (refer to [Section 7.2.9](#) for additional testing required).
- Two sequential hemoglobins <8.0 g/dL or a decrease of more than 30% from baseline value (defined above).
- Two sequential increases in serum creatinine >50% over the average of screening and baseline values (as defined above) OR an absolute increase in serum creatinine \geq 0.5mg/dL ($\geq 44.2 \mu\text{mol/L}$) over the average of screening and baseline values (as defined above)

AND

A confirmed (two sequential) CrCl decrease of >30% over the average of screening and baseline values (as defined above).

(N.B. Screening and baseline values to be used for this discontinuation criteria are defined at the beginning of [Appendix 8](#))

If the serum creatinine increase and the CrCl decrease have an identifiable and reversible cause (e.g. concomitant medication), then an additional retest may be considered after discussion with Sponsor study clinician or medical monitor. After retest, a decision for the subject to continue in the study will be made with the Sponsor study clinician or medical monitor.

- Other serious or severe AEs, after consultation with the Pfizer Medical Monitor. For example, subjects with a malignancy (exception of adequately treated or excised non-metastatic basal cell or squamous cell cancer of the skin or cervical carcinoma in situ) must be discontinued from the study. All malignancy events should be reported as serious AEs.

¹ In each case, there is a need for additional investigations, such as review of ethanol, recreational drug and dietary supplement consumption; testing for acute hepatitis A, B or C infection and biliary tract imaging should be promptly discussed with the Pfizer Medical Monitor.

Appendix 9. Evaluation Of Potentially Malignant Tumors, Suspicious Lymphadenopathy, Possible Extra-Nodal Lymphoproliferative Disorder (LPD)

The following steps should be taken in the event of potentially malignant tumors, suspicious lymphadenopathy or possible extra-nodal lymphoproliferative disorder (LPD) which might arise in the course of this study.

When there is a decision to biopsy a potentially malignant tumor, lymph node, or other tissue, the investigator and/or consultants should contact the Pfizer study team to discuss the issue and any decisions as soon as possible. It is recommended that specialists with experience in the evaluation of immunosuppressed subjects be consulted.

If a biopsy for lymphadenopathy or lymphoma is to be performed, the investigator or consultant should refer to the instructional slide deck in the Lymph Node Biopsy kit and review the following points with the surgeon and pathologist:

- Fine needle aspiration and core needle biopsy are strongly discouraged; excisional biopsy is required for accurate diagnosis.
- Tissue must be sent fresh to the pathology laboratory; the pathologist must be consulted before the procedure.
- Archive multiple frozen tissue samples, if possible.
- Include flow cytometry and cytogenetics as part of the pathologic evaluation.
- Culture for mycobacterium and fungi, if indicated.
- Collect and snap freeze peripheral blood lymphocytes for germ line evaluation (DNA).
- Archive multiple aliquots of serum samples.

For all biopsies, please request the pathologist to send the original slides used to make the definitive diagnosis, ancillary study reports, and the pathologist's report to the central laboratory for blinded review by central pathologists, to be paid for by Pfizer. Should the central pathologists make a diagnosis that is not essentially similar to the local pathologist's diagnosis, the local pathologist will be notified and provided with an opportunity to consult with the central pathologists (paid for by Pfizer). Translation during this consultation, if needed, will be provided by the staff of the Pfizer Country Office (PCO).

Both the local pathologist's diagnosis and the central pathologist's diagnosis will be reported in the study database.

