7.2.9. Laboratory Tests

Blood and urine samples will be collected at the time points identified in [Schedule of Activities](#) and [Section 6](#) the protocol. Unscheduled clinical labs may be obtained at any time during the study to assess any perceived safety concerns.

Protocol required testing includes hematology (CBC with differential), urinalysis, chemistry panel (sodium, potassium, chloride, bicarbonate, calcium, glucose, urea nitrogen, creatinine, creatine kinase, total protein, total bilirubin, direct and indirect bilirubin, alkaline phosphatase, gamma-glutamyl transferase, albumin, aspartate aminotransferase, alanine aminotransferase, and urine pregnancy testing (females of childbearing potential only).

Lipid Panel (cholesterol, indirect LDL, direct HDL, apolipoproteins A-1 and B, triglycerides) will be collected under fasting conditions, if possible, at the baseline visit for subjects who roll over more than 14 days after their EOS Visit from their qualifying/index study, every 6 months through year 5 and then every 12 months after year 5, and at the End of Study/Early Termination Visit for all subjects who enroll in this study.

Hepatitis B, Hepatitis C virus antibody (HCV Ab), and HIV-1/HIV-2 antibody screen will be obtained at the screening visit for subjects who enroll more than 14 days after their EOS Visit from their qualifying/index study.

In case of insufficient sample or issue on the sample quality (eg, hemolysis or clotting) the subject should return within 1 week to collect a new sample.

Creatinine clearance will be evaluated at every study visit using the Modified Schwartz equation or Cockcroft-Gault equation. ([Appendix 5](#))

Hepatitis B testing:

The blood sample will first be analyzed for HBsAg and HBcAb. If HBsAg is positive, the subject is excluded from the study. If the sample is HBsAg negative but HBcAb positive, the subject will be tested for HBsAb. If when tested, the HBsAb test is negative, the subject will be excluded from the study. Hepatitis B testing will not be performed in subjects determined to be HBs Ab positive in their qualifying study.

Hepatitis C testing:

HCV RNA is tested in case a positive HCV Ab result is obtained. Only subjects with negative HCV Ab or HCV RNA will be allowed to enroll in the study. To conserve blood volume at screening, HCV RNA sample collection may be deferred and collected only if required to confirm eligibility based on the HCV Ab results.

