Tofacitinib: The dose of tofacitinib may be decreased or discontinued for subjects who continue to have inactive disease for at least 24 consecutive weeks after receiving the last dose of MTX/leflunomide. The dose is to be reduced by 5 mg every 12 weeks as long as the subject's disease remains inactive. The evening dose should always be reduced before the morning dose. For example, a subject receiving a total daily dose (TDD) of 10 mg (5 mg BID) prior to tapering will step down to a TDD of 5 mg by taking 5 mg in the morning and 0 mg in the evening. If they continue to have inactive disease for a least 12 consecutive weeks while receiving a TDD of 5 mg, the 5 mg morning dose may also be discontinued.

Subjects will be followed for 6 months (24 weeks) after tofacitinib is discontinued by returning to the site for schedule visits and completing all visit assessments.

If at any time during the tapering process or after discontinuation of tofacitinib, the subject is not able to maintain the inactive disease status (as defined in the protocol [Section 7.1.7](#)), concomitant JIA therapies (eg, oral corticosteroid, methotrexate/leflunomide) and tofacitinib can resume if appropriate according to investigator judgment.

Tofacitinib will restart at 5 mg BID. Concomitant JIA therapies and doses should be adjusted at the discretion of the investigator.

Appendix 5. Estimated Glomerular Filtration Rate (GFR) and Creatinine Clearance (CrCl) Calculations

1. eGFR will be evaluated at screening to determine if a subject is eligible.

The Bedside Schwartz GFR equation²¹ will be used to estimate glomerular filtration rate (eGFR) from serum creatinine (creatinine methods with calibration traceable to IDMS).

$$\text{eGFR (mL/min/1.73 m}^2\text{)} = 0.413 \times (\text{Ht} / \text{Scr})$$

Height (Ht) in cm;

Serum creatinine (Scr) in mg/dL

2. Creatinine clearance (CrCl) will be evaluated at every study visit.

- (i) Participants <12 years of age

The Modified Schwartz equation²⁷ will be used to estimate creatinine clearance in participants < 12 years of age

$$\text{CrCl (mL/min/1.73 m}^2\text{)} = (\text{K} \times \text{Ht}) / \text{Scr}$$

K (proportionality constant):

Female Child < 12 years of age: K = 0.55

Male Child < 12 years of age: K = 0.70

- (ii) Participants ≥ 12 years of age

The Cockcroft-Gault equation²⁷ will be used to estimate the creatinine clearance for participants ≥ 12 years of age.

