Herpes zoster (shingles) is a painful rash that develops on one side of the face or body. The rash consists of blisters that typically scab over in 7 to 10 days. Before the rash appears, people often have pain, itching, or tingling in the area where it will develop. This may happen several days before the rash appears. Most commonly, the rash occurs in a single stripe around either the left or the right side of the body. In other cases, the rash occurs on one side of the face. Shingles on the face can affect the eye and cause vision loss. In rare cases (usually in people with weakened immune systems), the rash may be more widespread on the body and look similar to a chickenpox rash. Other symptoms of shingles can include: fever, headache, chills, and upset stomach.

Appendix 17. Summary of Changes from Original Protocol through Amendment 11

Document	Version Date	Summary of Change
Protocol Amendment 11	26 May2021	
Global Amendment
 
Protocol is amended as follows:
 
 • Protocol summary Section 3 study design: end of study text updated to clarify that subjects participation to the A3921145 study will end in 2 phases. • Schedule of Activities and Study Procedures Section 6.2.5 updated to clarify which procedures are required at the End of Study/Early Termination visit. • Addition of monitoring criteria related to Creatinine and Lipids increase for continuous assessment of subject's safety in the Appendix 8. • Creatinine discontinuation criteria wording updated in Appendix 8 to require two sequential increases in serum creatinine >50% over the average of screening/baseline and a confirmed creatinine clearance (CrCl) decrease of >30%. These updates are made to account for potential increases in creatinine due to physical activity, age and growth. CrCl added to the schedule of activities footnote and Section 7.2.9 laboratory tests. • Exclusion criterion #27 related to history of allergies, intolerance or hypersensitivity to lactose or CP-690,550 (tofacitinib): This country-specific exclusion criterion is made global to ensure consistent eligibility criteria for the study population. • Exclusion #8 is updated such that any infection requiring hospitalization, parenteral antimicrobial therapy or

090177e19a2c798c\Approved\Approved On: 18-May-2022 13:36 (GMT)

Document	Version Date	Summary of Change

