## 6. ANALYSES AND SUMMARIES

### 6.1. Primary Endpoints

The primary endpoints are standard laboratory safety data, adverse event (AE) reports, body weight, height and tanner stages. The Safety Analysis Set (SAS) will be used for analysis. For some endpoints, e.g., overall AE summary and AEs by SOC and PT, analyses will also be performed in sJIA2 analysis set and any additional summaries will be detailed in the programming plan.

All the safety data, including the following, will be summarized descriptively through appropriate data tabulations, descriptive statistics, and graphical presentations by visit:

- Adverse events will be summarized according to Pfizer standards.
- Safety laboratory tests will be summarized according to Pfizer standards.
- Subjects meeting certain cutoffs will be summarized for the following parameters: neutrophil counts, lymphocyte counts, serum creatinine levels, liver tests, lipid levels, hemoglobin.
- Subjects meeting discontinuation and monitoring criteria (see Protocol Appendix 8) will be summarized.
- Serious infections will be summarized.
- Incidence rate will be calculated for AEs of special interest. See Section [6.6](#) for details.
- For pubertal development as measured by Tanner Stage, a shift table of Tanner Stages from baseline to each post-baseline visit will be constructed by age group (2 to <6 years, 6 to <12 years, and 12 years or older) for males and females separately. The percentages in the shift table will be based on the number of subjects with available tanner stage data at both baseline and the post-baseline visit of interest.

- For assessment of growth as measured by body weight and height, a table of descriptive statistics for body weight and height standardized Z-scores (actual values and changes from baseline) at each visit will be constructed by age group (2 to <6 years, 6 to <12 years, and 12 years or older) for males and females separately.

Height (weight) Z-score is calculated using the following formulation:

$$Z = \frac{(X/M)^L - 1}{LS}, L \neq 0$$

Or

$$Z = \ln(X/M) / S, L = 0$$

where X is the physical measurement (e.g., height, weight) and L, M, and S are the values from standardized growth charts provided by the US Centers for Disease Control website (<http://www.cdc.gov/GrowthCharts/>) by gender for children from birth to 240 months. The Z-score cannot be calculated if age >240 months.

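### For a child who turns 12 after baseline, the >30% creatinine clearance criterion compares two different equations, so it can let growth-related creatinine rises through or hide a real fall

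*Protocol*

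**What the plan says.** Protocol 7.2.9 states: "Creatinine clearance will be evaluated at every study visit using the Modified Schwartz equation or Cockcroft-Gault equation". Appendix 5 assigns the equation by age. Modified Schwartz, K x height / serum creatinine in mL/min/1.73 m2, "will be used to estimate creatinine clearance in participants < 12 years of age", with K = 0.55 for girls and 0.70 for boys. Cockcroft-Gault, (140 - age) x weight / (72 x serum creatinine) in mL/min, times 0.85 if female, "will be used to estimate the creatinine clearance for participants ≥ 12 years of age".

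Appendix 8 fixes the reference value. For subjects enrolling more than 14 days after the index study: "For creatinine clearance, the average of A3921145 screening and baseline visit values will be used". For those enrolling on the same day or within 14 days: "For creatinine clearance, the average of qualifying/index study screening and baseline visit values will be used".

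Withdrawal needs two things together. One is a creatinine rise, either above 50% on two sequential tests or at least 0.5 mg/dL. The other is "A confirmed (two sequential) CrCl decrease of >30% over the average of screening and baseline values (as defined above"). The prompt-retest rule has the same structure with a single CrCl value. The Amendment 11 entry in Appendix 17 gives the reason for the revised criteria: "These updates are made to account for potential increases in creatinine due to physical activity, age and growth".

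SAP 6.1, under the primary endpoints, adds: "Subjects meeting discontinuation and monitoring criteria (see Protocol Appendix 8) will be summarized".

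**The concern.** The two equations differ in their body-size term and in their unit, and only one is indexed to body surface area. A percentage change from one to the other is not a change in renal function. Children may enter from age 2 and the visit schedule runs to Month 120, so crossing 12 on study is foreseeable.

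The CrCl criterion is there to sort children whose creatinine has already risen. With one height-based equation, growth offsets part of the rise, and a rise explained by growth does not count. Across equations the result depends on weight for height at the later visit. A lighter child can be withdrawn for a rise the criterion was meant to excuse. A heavy child can stay below the threshold despite a fall that the baseline equation would show. The same errors enter the retest rule and the SAP count of subjects meeting the Appendix 8 criteria.

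**Working it through.** The documents state no CrCl figure to reproduce. The equations and thresholds come from Appendices 5 and 8. All heights and creatinine values are assumptions, as are all weights except the 38.3-70.9 kg range of the 12 to <18 cohort in Protocol Table 1 (n = 8).

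**Step 1: the switch alone.** At equal creatinine, k = Cockcroft-Gault / Schwartz, with W in kg and H in cm:
- Boys, age 12: (128W/72) / (0.70H) = 2.540 W/H. At age 13: 2.520 W/H.
- Girls, age 12: (0.85 x 128W/72) / (0.55H) = 2.747 W/H. At age 13: 2.726 W/H.

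| Child, age 12 | k - 1 |
|---|---|
| Boy, 150 cm, 40 kg | -32% |
| Boy, 155 cm, 80 kg | +31% |
| Boy, 150 cm, 38.3 to 70.9 kg | -35% to +20% |
| Girl, 150 cm, 38.3 to 70.9 kg | -30% to +30% |

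**Step 2: when each criterion is met.** Let g be the height ratio and r the creatinine ratio, visit over baseline.
- Creatinine criterion (percentage form): r > 1.50.
- CrCl criterion, Schwartz at both times: g/r < 0.70, so r > g/0.70.
- CrCl criterion across equations: r > g x k/0.70.

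With one equation, the CrCl criterion filters something only if g/0.70 > 1.50, that is, if height has grown by more than 5%. Across equations the filter is fully lost when g x k/0.70 <= 1.50, so k <= 1.05/g. Rises then wrongly passed:
- g = 1.05: none (1.05/0.70 = 1.50).
- g = 1.10: +50% to +57%, if k <= 0.955. At 13 years and 155 cm that is below about 58.7 kg (boy) or 54.3 kg (girl).
- g = 1.165: +50% to +66%, if k <= 0.901. At the same age and height, below about 55.4 kg (boy) or 51.2 kg (girl).

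**Step 3: filter lost.** Boy, baseline 133 cm and creatinine 0.40 mg/dL; at 13, 155 cm and 45 kg. Here g = 155/133 = 1.165 and k = 2.520 x 45/155 = 0.732. The thresholds are r > 1.665 with Schwartz twice and r > 1.218 across equations. Baseline CrCl = 0.70 x 133/0.40 = 232.75.

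| Creatinine (mg/dL) | Rise | Schwartz at visit | Cockcroft-Gault at visit |
|---|---|---|---|
| 0.61 | +52.5% | 177.9 (-23.6%), not met | 130.1 (-44.1%), met |
| 0.66 | +65% | 164.4 (-29.4%), not met | 120.3 (-48.3%), met |
| 0.67 | +67.5% | 161.9 (-30.4%), met | 118.5 (-49.1%), met |

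**Step 4: fall missed.** Boy, 140 to 155 cm, age 13: g = 155/140 = 1.107, so Schwartz twice is met at r > 1.582.
- 70.9 kg: k = 1.153, so the cross-equation criterion needs r > 1.823. Rises of about +58% to +82% are missed.
- 80 kg: k = 1.301, r > 2.057. Rises of about +58% to +106% are missed.

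**Step 5: Cockcroft-Gault at both times.** Boy, 30 kg, age 9, creatinine 0.40: 131 x 30/(72 x 0.40) = 136.5. At 45 kg, age 13, creatinine 0.61: 127 x 45/(72 x 0.61) = 130.1. The change is -5% although creatinine rose 52.5%, because weight gain absorbs it.

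**The case against.** The case against acting is about reach and consequence.

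- **Route.** Protocol 6.1 makes rollover within 14 days the usual path. Those baselines come from the index study, whose equation is not given here. This stands: for rollovers the defect is an unspecified derivation, although Appendix 5's age rule suggests the same mix. For later enrollers the mix follows directly.
- **Numbers.** The criterion dates from Amendment 11 (May 2021). Subjects from A3921103 and A3921104 leave after the first pJIA approval, and Protocol 1.1 already reports US and EU approval. Planned enrolment rose from about 290 to 340 when A3921165 was added, suggesting roughly 50 children, and the study ends once all of them have about 1 year. Short follow-up means little growth, and at 5% growth no rise is wrongly passed. Few children may be affected prospectively.
- **Narrow or extreme cases.** At 10% growth from 0.40 mg/dL the false-trigger band is only above 0.60 and up to about 0.63. The missed-fall examples imply high BMI: 80/1.55² = 33.3. At some intermediate weights the two equations agree. All true; these bear on frequency.
- **Other safeguards.** Protocol 6.2.6 requires retesting every one to two weeks after a confirmed creatinine rise above 33%, with no CrCl condition, so a missed fall would still be followed clinically. That softens the second error. It does not undo a withdrawal triggered by the first, and the extra retest Appendix 8 allows for a reversible cause would repeat the same cross-equation comparison.
- **Purpose.** The Amendment 11 rationale covers the two-sequential-creatinine requirement as well and also names physical activity. Age and growth are nevertheless in it, and the height term in Schwartz is what allows for growth.
- **Analysis.** No hypothesis is tested. Creatinine cutoffs and renal-event incidence rates do not use this criterion.

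**Conclusion.** The concern holds. For a child enrolled more than 14 days after the index study who was under 12 at baseline and is 12 or older at the visit, the rule as written compares values from different equations in different units. For rollovers within 14 days, the derivation of the reference value is unspecified.

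Under the assumed body sizes, the switch alone can be as large as the 30% threshold, in either direction depending on weight. It cannot trigger withdrawal alone, because the creatinine criterion must also be met. Its effect is confined to children with a qualifying creatinine rise: wrongly passed rises of up to +57% at 10% height growth and +66% at 16.5%, and missed rises of up to +82% or +106% in the two heavy examples, taking Schwartz at both times as the comparator. The share of subjects affected cannot be derived from the documents.

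This should be fixed. It touches individual retest and withdrawal decisions and one descriptive count among the primary safety summaries; no other planned analysis depends on it.

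**What to change.** State in Appendices 5 and 8 that, within a subject, baseline and visit CrCl are calculated with the same equation and unit, including when the baseline comes from the index study.

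For children under 12 at baseline, keep a height-based, indexed equation throughout. Cockcroft-Gault at both times would be consistent but can hide a decline behind weight gain (Step 5). Appendix 5 defines the Schwartz K only below 12, but a constant held fixed within a subject cancels from the percentage change. The Bedside Schwartz form already in Appendix 5 would therefore give the same result.

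In SAP 6.1, derive the count of subjects meeting Appendix 8 criteria on this basis and list each subject whose classification differs, in either direction, from the rule as written.

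The cost is one sentence in the two protocol appendices and one SAP derivation rule. Height, weight and creatinine are already collected. The SAP change is worth making even if few children remain under prospective monitoring.
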